2.2.2. Economic Aims and Objectives

An economic evaluation will be undertaken to assess the cost-effectiveness of no treatment versus full dose anticoagulation in patients with ISSPE. The base-case evaluation will take the form of an incremental cost-utility analysis to estimate cost per quality adjusted life year (QALY) over a 24 week follow up and a cost-effectiveness analysis to estimate cost per VTE avoided over 52 weeks using routine data sources. Both analyses will be from a health services perspective. Additional analysis, using decision modelling, will explore the cost-utility and cost-effectiveness of a pragmatic treatment policy (without expert thoracic radiological review) over a 52 week time horizon.

2.2.3. Mechanistic (behavioural) Aims and Objectives

- 1. To determine whether not treating SSPE is acceptable to patients and clinicians.
- 2. To determine the health seeking behaviours and health utilisation of a no anticoagulation treatment strategy for isolated SSPE.

3. TRIAL DESIGN AND SETTING

3.1.Trial Design

STOP-APE is an investigator led, multicentre, prospective, randomised controlled, open-label, pragmatic clinical trial with central, blinded, independent adjudication committee (CIAC) endpoint assessment over 3 months for efficacy of withholding anticoagulation for ISSPE. The trial is designed to test the superiority for bleeding events and non-inferiority for recurrent VTE.

Participants will be randomised to either the control arm: full dose anticoagulant treatment as standard care, or the intervention arm: withholding anticoagulation. The choice of anticoagulant will be determined by the responsible treating clinician as part of the standard of care. Pre-randomisation empirical anticoagulation treatment will be allowed for up to 7 days immediately prior to randomisation.

The joint (multiple) primary outcomes of recurrent VTE and clinically relevant bleeding will be established from the trial site clinical notes and electronic health records, patient trial follow-ups and centralised data from hospital episode statistics (HES). The local research team will conduct a safety telephone follow up at 4 weeks, with a permitted window of 1 week either side. Trial follow-ups at 12 and 24 weeks will be performed by the local research team via telephone to complete case report forms and questionnaires. A window of \pm 2 weeks will be permitted for follow-ups.

A 12-month internal pilot will assess feasibility and acceptability with safety of randomisation based on acute reporting radiologists' diagnoses, assessed as part of a nested CTPA study. Note: The nested CTPA study will not stop after the 12-month internal pilot phase and so will be conducted for the full duration of the trial.

3.2. Trial Setting

Participants will be recruited from approximately 50 trial sites from secondary care clinical settings of emergency departments, ambulatory care and acute medical units within NHS hospitals in the UK. The recruitment rates will be assessed during the pilot phase and additional sites will be recruited if required (see section 2.1).

3.3. Identification of participants

Patients aged 18 years or over with ISSPE will be enrolled into the STOP-APE trial. Potential trial participants will be identified from participating centres, in the UK, by members of their normal clinical team via the following two routes:

1. Adult patients presenting at secondary care clinical settings of emergency departments, ambulatory care units and acute medical units with acute symptomatic SSPE diagnosed with CT pulmonary angiogram/CT thorax with IV contrast.

2. Radiology departments who can flag patients to the research team where they identify SSPE as an incidental diagnosis on a contrast enhanced scan undertaken as part of surveillance after any active treatment for cancer.

In order to retain the pragmatic nature of the trial and to ensure generalisability of results, detailed diagnostic criteria for SSPE will not be issued to general radiology departments. However, an audit of CTPA reports showed that in 15% of PE reports, the arterial distribution is not specified (a binary report is given of 'positive for PE'). Therefore, simple guidance will be issued to radiology departments to specify arterial distribution of PE as either sub-segmental (in which case patients can be considered for potential inclusion in the trial), or at least segmental in size (in which case patients do not meet recruitment criteria).

Patients identified via either of the above routes will be referred to the research team for confirmation of full eligibility. It is the responsibility of the PI or suitably qualified delegate in accordance with local practice as identified on the Site Signature and Delegation Log to confirm eligibility.

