Clinically relevant non- major bleeding (CRNMB)	Any sign or symptom of haemorrhage (e.g., more bleeding than would be expected for a clinical circumstance, including bleeding found by imaging alone) that does not fit the criteria for the ISTH definition of major bleeding but does meet at least one of the following criteria: i. requiring medical intervention by a healthcare professional ii. leading to hospitalisation or increased level of care

	iii. prompting a face to face (i.e., not just a telephone or electronic communication) evaluation ISTH major bleeding in non-surgical patients is defined as having a symptomatic presentation and: iv. Fatal bleeding, and/or v. Bleeding in a critical area or organ, such as intracranial, intraspinal, intraocular, retroperitoneal, intra-articular or pericardial, or intramuscular with compartment syndrome, and/or vi. Bleeding causing a fall in haemoglobin level of 20 g L ⁻¹ (1.24 mmol L ⁻¹) or more or leading to transfusion of two or more units of whole blood or red cells.	
Net clinical benefit	Composite of recurrent VTE and clinically relevant bleeding events.	
Active cancer	Cancer diagnosed within the past 6 months, cancer for which anticancer treatment was being given at the time of enrolment or during 6 months before randomisation, or recurrent locally advanced or metastatic cancer.	
Withholding	In relation to this trial withholding is defined as stopping the current treatment strategy of anticoagulation for at least 3 months.	

TRIAL SUMMARY

Title:

STOPping Anticoagulation for isolated or incidental subsegmental Pulmonary Embolism (STOP-APE)

Primary objective:

To determine if withholding anticoagulation is non-inferior to standard anticoagulation therapy in the treatment of isolated subsegmental pulmonary embolism (ISSPE) for preventing recurrent venous thromboembolism (VTE), or death related VTE, or superior for clinically relevant bleeding over 3 months, compared with at least 3 months of full anticoagulation.

Secondary objectives:

- Determine whether withholding anticoagulation for isolated subsegmental PE reduces harm (recurrent VTE, bleeding events) compared with at least 3 months of full anticoagulation at 6 and 12 months and impact on diagnoses of pulmonary hypertension at 12 months.
- Determine the reclassification rate of SSPE diagnoses made by acute reporting radiologists when reviewed by thoracic radiologists and formulate a set of rules to improve acute reporting radiologists' diagnoses of SSPE.

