1. BACKGROUND AND RATIONALE

1.1.Background

Pulmonary embolism (PE) is a potentially serious condition, whereby blood clots cause a blockage of the blood supply to the lungs. PEs are often caused by blood clots in the legs and occasionally the arms (deep vein thrombosis (DVT)) breaking off and travelling to the lungs. A number of risk factors increase the chances of developing PE and/or DVT, including cancer, major surgery, pregnancy, some medications (e.g. the combined oral contraceptive pill or hormone replacement therapy), dehydration, long-distance travel and prolonged immobility. The symptoms of a PE depend on the size and location of the blood clot. A large PE can cause symptoms of breathlessness and chest pain, and the diagnosis is made using blood tests and a scan of the lungs. The treatment of PE includes anticoagulant medication ("blood thinners") that are taken over months and include: warfarin, an injectable form of heparin and direct oral anticoagulants (DOACs). These medications work by preventing new clots from forming whilst the body's own mechanisms break down the clots.

Acute pulmonary embolism (PE) is associated with significant mortality and morbidity and has a wide range of clinical severity from sudden death or haemodynamic instability through to no symptoms. The increased use and improving sensitivity of computed tomography (CT) imaging has resulted in a large increase in identification of both subsegmental PE (SSPE; embolism confined to subsegmental pulmonary vasculature) as well as incidental PE (when the CT was performed for indications other than identification of venous thromboembolism (VTE)).

To date, there have been no randomised trials to assess how subsegmental emboli should be managed, and current guidelines are based on non-randomised studies and clinical consensus. Anticoagulation of these patients may reduce short or longer term thromboembolic risk but this must be balanced against the potential increased risk of major and potentially life threatening bleeding which can occur with anticoagulant therapy.

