1.2.3. Choice of intervention

This trial is testing how a strategy of withholding anticoagulation in ISSPE (either symptomatic or incidental) for at least 3 months compares to standard care which is full anticoagulation for at least 3 months. We have not specified the choice of anticoagulation as there are contra-indications for directly acting oral anticoagulants (DOACs) such as renal impairment where warfarin would be an acceptable alternative. In some patients, low molecular weight heparin (LMWH) injected subcutaneously would also be appropriate. By not specifying the drug class of anticoagulation, we are testing the strategy of full anticoagulation against the strategy of no anticoagulation in the most generalisable and pragmatic way.

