6.4. Randomisation

6.4.1. Randomisation Methodology

Participants will be randomised by computer at the level of the individual in a 1:1 ratio to either intervention (withhold anticoagulation treatment) or control (full dose anticoagulation treatment as standard of care) arm.

A minimisation algorithm will be used within the online randomisation system to ensure balance in the treatment allocation over the following variables:

- Age (<50, 50-70, >70 years)
- Cancer (Yes/No)
- Clinically suspected or confirmed COVID-19 (Yes/No)
- Type of SSPE (Symptomatic / Incidental)
- Previous clinically relevant bleeding as defined by the International Society on Thrombosis and Haemostasis (ISTH) (Yes/No)
- Randomising site

A 'random element' will be included in the minimisation algorithm, so that each participant has a probability (unspecified here), of being randomised to the opposite treatment that they would have otherwise received.

Full details of the randomisation specification will be stored in a confidential document at the Trial Office.

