13.2.3. Subgroup Analyses

Subgroup analyses will be limited to the same variables used in the minimisation algorithm excluding centre (see section 6.2). Tests for statistical heterogeneity (e.g. by including the treatment group by subgroup interaction parameter in the statistical model) will be performed alongside the effect estimate within subgroups. The results of subgroup analyses will be treated with caution and will be used for the purposes of hypothesis generation only.

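### Section 3.3 finds incidental SSPE only on cancer-surveillance scans, which is narrower than the protocol's own definition, title and eligibility criteria

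*Protocol*

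**What the plan says.** Protocol Section 3.3 states that potential participants will be identified "by members of their normal clinical team via the following two routes". Route 1 covers adults presenting to emergency, ambulatory care and acute medical units with "acute symptomatic SSPE diagnosed with CT pulmonary angiogram/CT thorax with IV contrast". Route 2 has radiology departments flag patients "where they identify SSPE as an incidental diagnosis on a contrast enhanced scan undertaken as part of surveillance after any active treatment for cancer". The section then refers patients found by either route to the research team. It names no third route and does not present the two as examples.

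Other parts of the protocol use a wider notion of incidental:

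- Section 1.1 speaks of "incidental PE (when the CT was performed for indications other than identification of venous thromboembolism (VTE", a meaning with no link to cancer.
- The Definitions table describes SSPE as symptomatic or incidental, without a cancer condition.
- The title names incidental SSPE without restriction.
- Section 1.2.3 says the trial tests "withholding anticoagulation in ISSPE (either symptomatic or incidental) for at least 3 months".
- Sections 4.1 and 4.2 admit any SSPE on CTPA or contrast CT thorax, subject to the other criteria. They exclude active cancer and do not require a cancer history for incidental cases.

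Section 6.4.1 lists cancer (yes/no) and type of SSPE (symptomatic or incidental) as separate minimisation factors. Section 13.2.3 adds: "Subgroup analyses will be limited to the same variables used in the minimisation algorithm excluding centre". Both factors are therefore planned subgroups, and the same section treats subgroup results as hypothesis-generating.

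**The concern.** A clinically stable outpatient whose subsegmental embolus is seen on a contrast CT done for, say, lung disease or aortic imaging meets the inclusion criteria. Section 3.3 gives that patient no way in. Nothing in Section 1.2.1, which justifies the population, explains why incidental cases should come only from cancer follow-up, so the limit does not read as a deliberate choice of scope.

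Three things are at stake. The trial's findings would naturally be read as covering incidental SSPE in general when no incidental patient without a cancer history stands behind them. The planned comparison of effects in symptomatic and incidental SSPE would largely be a comparison between patients without and with past cancer. And the loss would not show in the trial's own records: Section 3.3.2 asks sites to count patients by exclusion factor and patients who decline, and a patient never flagged is neither. No later analysis can recover them.

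**Working it through.** **1. The four cells under the routes as written.** Cancer = yes is read here as a history of non-active cancer, because active cancer is excluded and Section 6.4.1 does not define the factor.

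| | Cancer = no | Cancer = yes |
|---|---|---|
| Symptomatic | route 1 | route 1 |
| Incidental | no route | route 2 |

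So P(cancer | incidental) = 1. The reverse does not follow. Section 1.2.1 makes patients with non-active cancer eligible whatever their presentation, so symptomatic patients with past cancer can enter by route 1.

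**2. How strongly the two factors are tied.** The protocol gives neither the incidental share of recruits, f, nor the share of symptomatic recruits with past cancer, c. Both are assumed. With incidental nested in cancer:

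- P(cancer) = f + (1 − f)c
- P(incidental | cancer) = f / P(cancer)
- phi = f(1 − P(cancer)) / √[f(1 − f) P(cancer)(1 − P(cancer))]

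Example, f = 10% and c = 5%: P(cancer) = 0.10 + 0.90 × 0.05 = 0.145; P(incidental | cancer) = 0.10/0.145 = 0.69; phi = 0.0855/√(0.09 × 0.145 × 0.855) = 0.81.

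| f | c | P(incidental given cancer) | phi | Symptomatic with cancer, of 1320 |
|---|---|---|---|---|
| 10% | 5% | 0.69 | 0.81 | 59 |
| 10% | 20% | 0.36 | 0.53 | 238 |
| 30% | 5% | 0.90 | 0.92 | 46 |
| 30% | 20% | 0.68 | 0.74 | 185 |

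The last column is 1320 × (1 − f) × c. These are the only patients against whom incidental SSPE can be compared with cancer history held constant. The factors coincide (phi = 1) only if c = 0.

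**3. What the subgroup could have shown in any case.** The plan's own sizes in Section 13.1 reproduce:

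- Bleeding, 7% v 3%, two-sided 0.05, 90% power: [1.96√(2 × 0.05 × 0.95) + 1.2816√(0.07 × 0.93 + 0.03 × 0.97)]² / 0.04² gives 622 per arm, 1244 in total.
- VTE, 2% in both arms, margin 2.5 points, one-sided 0.025, 90% power: (1.96 + 1.2816)² × 2 × 0.02 × 0.98 / 0.025² gives 660 per arm, 1320 in total.

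The same assumptions applied within an incidental subgroup of 1320f evaluable patients give:

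| f | Per arm | Power, VTE margin | Power, bleeding |
|---|---|---|---|
| 5% | 33 | 11% | 11% |
| 10% | 66 | 18% | 18% |
| 20% | 132 | 31% | 32% |
| 30% | 198 | 43% | 45% |

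Example, f = 10%: SE = √(2 × 0.02 × 0.98/66) = 0.0244; 0.025/0.0244 − 1.96 = −0.93; power 18%.

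A confirmatory answer for incidental SSPE alone was never within the design, whichever scans supply the patients.

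**4. Effect on the primary analysis.** Allocation is randomised within whatever population is enrolled. Correlation between two minimisation factors does not bias the treatment comparison. What changes is whom the result describes.

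**The case against.** The strongest reply is that routes of identification are not eligibility criteria. Section 4.1 admits an incidental patient without cancer, nothing forbids a site from randomising one, and the guidance to radiology departments in Sections 3.3 and 3.3.1 asks only for the arterial level of the embolus and says subsegmental cases can be considered. In part this stands: some sites may recruit beyond the two routes. But that guidance concerns how a scan is reported. It does not set up another referral path, and Section 3.3 sends forward patients found by the two routes.

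A second reply is that the protocol names active treatment as the main driver of VTE risk in cancer and excludes active cancer, so survivors under surveillance may differ little in risk from other patients. That is fair. It limits the likely size of the confounding but does not supply the missing patients. The hospital-admission exclusion would also remove some of those with incidental findings on other scans.

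A reader might infer two stronger things. One is that incidental becomes a synonym for cancer. The protocol does not support this, because the nesting runs one way: symptomatic patients with past cancer can enter, and the two presentations can be compared among them. The other is that the trial cannot answer its question. The primary objective concerns isolated SSPE as a whole, no objective or power statement is specific to incidental SSPE, and subgroups are exploratory. Nor is it a defect here that the protocol sets no rule for splitting the incidental subgroup by cancer or for small cells; that detail belongs in the statistical analysis plan.

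**Conclusion.** The inconsistency is real. Section 3.3 is narrower than the protocol's definition, title, tested strategy and eligibility criteria, and no reason is given. If sites follow it, all incidental participants have a cancer history, the symptomatic/incidental subgroup is confounded with cancer except among patients with a cancer history, and findings cannot be extended to incidental SSPE found outside cancer surveillance.

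The size is only partly known. The empty cell follows from the wording, provided sites keep to the two routes. The correlation of 0.53 to 0.92 rests on assumed shares. The number of eligible patients missed cannot be estimated from the protocol. The primary randomised comparison for isolated SSPE overall is unaffected. This is a cheap improvement, not a flaw in the main inference.

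**What to change.** Reword route 2 in Section 3.3 along these lines: *SSPE found incidentally on any contrast-enhanced CT thorax performed for an indication other than suspected VTE, including surveillance after cancer treatment*. Align the guidance issued to radiology departments with it. The eligibility criteria and the sample size stay as they are.

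If the limit to cancer follow-up is intended, say so and give the reason, and restrict the stated scope of incidental SSPE to cancer-surveillance patients in the title, objectives and conclusions.

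The first option costs one sentence, a matching line in the guidance, and somewhat more flagging by radiology departments. It helps only if made before or during recruitment. The second costs text changes and a narrower claim.

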3.3.1. Nested Computed Tomography Pulmonary Angiogram (CTPA) study

We will conduct a nested study of CTPAs within this trial for four purposes:

1. Safety assessment during Internal Pilot

SSPE is diagnosed at acute presentation by radiologists with a spectrum of expertise in thoracic imaging. There have been no studies on the accuracy of acute reporting radiologists' interpretation of CTPA scans for SSPE compared with thoracic radiologists using a standard reporting checklist. Disagreement could arise because

- a. artefact (e.g. from breathing) may be misinterpreted as a filling defect due to PE leading to a false positive diagnosis of SSPE.
- b. because PE is present but is in fact affecting larger vessels (e.g. segmental or lobar) in which case patients should be given full anticoagulation.

The greater risk to patients is where larger vessel PE is misclassified as SSPE as these patients will have a 50% chance of receiving no anticoagulation in this trial and it is therefore crucial that this potential misclassification is detected as soon as possible. After recruitment and randomisation into the trial which is based on the acute reporting radiologist's diagnosis of SSPE, the CTPA will be subject to an initial safety check within 48 hours by a trial thoracic radiologist using a structured reporting template. This will continue for the entire duration of the study.

We have not opted to have expert review of the CTPA scan prior to randomisation in order to deliver the trial within a pragmatic framework of acute clinical care, minimising barriers to recruitment and also yielding important information about the impact of applying trial results with general acute reporting radiologists determining the presence of SSPE. The design of recruitment prior to expert review balances the minimisation of barriers to recruitment with rapid detection of low prevalence misclassification through early discontinuation of an inappropriate treatment arm but continuation in the trial.

Protocol for review of CTPA

i. Reporting guidance

We will issue simple guidance for radiology departments at recruiting sites to specify arterial distribution of PE as either sub-segmental (in which case patients can be considered for potential inclusion in the trial), or at least segmental in size (in which case patients do not meet recruitment criteria).

ii. Mechanism of CTPA retrieval

Each patient that is initially registered in the trial (consented prior to ultrasonography of the legs) will have their CTPA tagged with a study identifier and then uploaded to a cloud based Picture Archiving and Communication System (PACS) system which will be remotely accessed by trial thoracic radiologists. A database will be set up within the Bath Hospital Radiology department to receive the CTPA scans from the cloud based PACS for long term storage.

iii. Reading of CTPA images and communication to trial sites

The cloud based PACS will be used for image presentation to trial radiologist reviewers. They will log on through a secure portal and rate the scans using a standard case report form which will include the largest order of arterial vessel containing a filling defect, an assessment of clot burden, if artefact is present mimicking the presence of SSPE, pulmonary artery size, right sided cardiac dimensions and parenchymal lung changes. Each CTPA will be reviewed by two thoracic radiologists who will be blinded to each other's review.

In the unlikely event that segmental vessels or larger contain filling defect (as detected by either reviewer), then this will be communicated immediately to a central clinical coordinator who will then immediately contact the patient to make them aware that they need to attend hospital immediately, in addition to the local research team (or on call acute medical team at the weekend) who will make an assessment with regards to treatment with anticoagulation as part of standard of care (as this is a prospective randomised open blinded end-point study design, the prescribing of anticoagulation will be in the hospital discharge summary).

For patients found not to have SSPE on review of their CTPA this will be fed back to their clinical treating team who will make an assessment with regards to treatment as part of standard of care. Patients will continue in the trial and be followed up as per the trial protocol.

The data to be collected and stored in PACS from CTPAs by each trial radiologist are as follows:

- 1. Breathing artefact (categorised into 4 levels)
- 2. Thrombus distribution, burden and location (if thrombus is present)
- 3. At thrombus level size of upstream/downstream vessel, contrast density, signs of artefact.
- 4. CT quality
- 5. Protocol variations, dose and technique across sites
- 6. Cardiac calcifications (Aortic Valve, Mitral Valve, coronary arteries)

- 7. Size of Pulmonary Artery, Right Atrium, Right Ventricle, Left Atrium, Left Ventricle, (including ratio or right ventricle / left ventricle) and Aorta.
- 8. Grading of an emphysema present using a standardised system
- 9. Changes consistent with COVID-19 infection
- 10. Incidental findings

2. Reclassification rate from thoracic radiologist review

After 500 CTPA scans, we will determine the agreement between thoracic radiologist review and initial acute reporting radiologist's diagnosis. Where two thoracic radiologists disagree about the presence of SSPE, a third review will be used to achieve consensus. At this stage, we will determine if, in spite of adequate recruitment to the trial based on our initial powering, we may need to increase the recruitment target due to reclassification of patients and a reduction in the number of 'true SSPE' scans. We will maintain power in the trial for the non-inferiority outcome by applying our recruitment target to the numbers of patients with true SSPE. The DMC will advise on changes to total recruitment based on an interim analysis. If recruitment is green, and rate of site initiation is linear, we will increase the number of sites in order to increase recruitment target to a rate feasible as determined by the DMC and TSC.

3. Determine a set of diagnostic criteria for SSPE

At the end of the trial, pragmatic guidelines will be drawn up through consensus meetings of the thoracic radiologists reporting the trial CTPAs. These can then be utilised in subsequent radiological reporting practice to improve diagnosis of SSPE in routine emergency care as well as in future research studies where SSPE are reported.

4. Future artificial intelligence studies

The trial database will be used for automated image analysis and artificial intelligence (AI) studies (not charged to this grant). Potential applications of the CTPA images with clinical correlation are to investigate risk of recurrent VTE in patients without anticoagulation, to train automated algorithms to diagnose SSPE and to act as clinical decision support so that larger vessel PE is not mis-classified as SSPE.

